An Open Label Trial of Bupropion and Naltrexone for Binge Drinking

NCT number NCT02842073
Document Date 05-15-2018

Study Protocol

An Open Label Trial of Bupropion and Naltrexone for Binge Drinking

Overall Concept: The current proposal represents an innovative pharmacological approach to the treatment of binge drinking that derives from preclinical findings from the laboratory of [name], one of the proposal's consultants. [name] found that a melanocortin agonist, melanotan II, potently suppresses binge drinking (Navarro et al, 2015) in a mouse model of binge drinking. Because the antidepressant bupropion has been shown to activate melanocortin systems in brain (Greenway et al, 2009) [name] lab also studied the effect of bupropion on binge-drinking in their model and showed that bupropion significantly reduced binge-drinking at doses that were lower than those that suppress appetite (unpublished data). Because bupropion is a clinically available and FDA approved medication [name] initiated a discussion with our group to consider a clinical trial of bupropion for binge drinking. Navarro et al (2015) found evidence that using a melanocortin agonist with an opioid antagonist such as naltrexone enhanced the potency of the opioid antagonist to suppress binge drinking. In addition to a direct effect on binge drinking, [name] lab has proposed that modulating the melanocortin system and counteracting binge drinking may have value in *preventing* progression of alcohol use from binge drinking to dependent level drinking (Thiele, 2012; Navarro et al, 2015)—potentially, a very important finding for clinical care.

General Background: Binge drinking is a major public health problem in the United States. The Center for Disease Control (CDC) places alcohol as the number three cause of preventable deaths following nicotine use and overweight (Mokdad et al, 2004). Binge drinking, generally defined as the consumption of five or more standard drinks for a man or four or more drinks for a woman in about a two hour period (see Courtney and Polich 2009), is a major component of excessive alcohol use and a serious problem for the United States. The CDC (2012) report indicated that 17.1% of the adult U.S. population reported one binge drinking episode in the past 30 days in 2010--men (23.2%) vs. women (11.4%) with peak ages 18-24 years (28.2%), 25-34 years (27.9%), and 35-44 years (19.2%). Men reported an average of 5 binge drinking episodes/month with a mean of 9.0 drinks/episode and women 3.2 binge drinking episodes/month at 5.9 drinks/episode. Binge drinking leads to multiple problems, e.g. accidental injury (Gmel et al, 2006), aggressive and violent behavior (Shepard et al, 2006), and high blood pressure (Fan et al, 2008). Additionally, there is increased risk for developing alcohol dependence in individuals that binge drink frequently (Hingson et al, 2006). Overall, binge drinking contributes to more than half of all deaths attributed to alcohol and to three quarters of the economic cost of excessive alcohol use—*binge drinking is a serious public health problem and one that may exceed traditionally defined alcohol dependence in its overall cost to society.*

Binge drinking is a complex construct as it is both a stand-alone phenomenon and also a component of alcohol use disorders. We are focusing on the behavior to allow greater fidelity to the preclinical data where the key behavior was consumption of an intoxicating amount of alcohol in a two hour period, a non-dependent model (Navarro et al, 2015). The majority of binge drinkers do not have physical dependence (see Woerle et al, 2007), and we are particularly interested in this “developmental” phase towards overt physical dependence as the preclinical literature suggests this phase may be a key time for clinical intervention (Thiele 2012).

Treatment of Binge Drinking with or without Co-Occurring Alcohol Use Disorders

Despite the significant economic and personal costs associated with binge drinking, efforts to improve recognition and treatment of binge drinking have received less attention than efforts directed towards DSM-IV defined alcohol dependence though this is beginning to change (Siqueira and Smith, 2015). A recent assessment of screening and brief intervention for patients with risky drinking (where many binge drinkers are categorized) and related alcohol-use problems in the primary care setting revealed that a variety of brief intervention techniques, e.g. brief advice, motivational interviews, can reduce heavy drinking episodes (12% more individuals with no heavy drinking, 95% CI 7-16%) (Jonas et al, 2012). Unfortunately, the improvements were modest and health impacts were unclear highlighting the need for additional approaches such as pharmacotherapy. As noted by Hester (2015) "...they [non-dependent drinkers] are an underserved patient population associated with significant and growing health care costs." The availability of medication options for binge drinking would increase medical clinicians' interest in identifying and treating this significant problem.

Pharmacotherapy approaches to treat binge drinking: Few clinical trials for binge drinking per se have been completed. O'Malley et al (2015) studied 128 young adult college students with heavy drinking (≥ 4 heavy drinking days in 4 weeks; ~60% DSM-IV alcohol dependent but without physical dependence) and compared 25 mg daily + 25 mg targeted naltrexone to be taken in anticipation of a heavy drinking episode to placebo. They did not find evidence for an effect on %heavy drinking or %abstinence but naltrexone led to a reduction in drinks/drinking day. They noted, "...the risk-benefit ratio favors offering young adult drinkers naltrexone to reduce the amount of alcohol they drink." Three trials have been conducted for older heavy drinkers or problem drinkers, mean age late 40's, using the opioid antagonists naltrexone (Kranzler et al 2003, 2009) or nalmefene (Karhuvaara et al, 2007). These trials sought individuals who were problem drinkers or heavy drinkers rather than physically dependent on alcohol, though 84-95% met criteria for DSM-IV alcohol dependence. These trials excluded individuals with evidence of more severe alcohol dependence, i.e. >4 DSM-IV criteria for dependence or having a history of alcohol withdrawal. All three trials found evidence for modest benefit. Taken together, these studies indicate that medications can be effective in the treatment of the milder end of the spectrum of alcohol use disorders where many binge drinkers are categorized. Pharmacotherapy for binge drinking is clearly in its infancy, perhaps in a similar state to pharmacotherapy for traditionally defined alcohol dependence 20 years ago when naltrexone was first discovered.

The current proposal will conduct the first human trial to test the novel preclinical finding that activating melanocortin systems in brain with/without opioid blockade potently reduces binge drinking. Identification of a potential efficacy signal would be significant as it would not only demonstrate that activation of melanocortin systems with/without opioid blockade has potential for therapeutic application for binge drinking in humans but would increase awareness of a biomedical component of binge drinking which could positively affect medical clinicians' attitudes and potentially increase identification and treatment efforts.

Innovation

The present application is innovative in two major areas: *1) it represents the first clinical test of the exciting preclinical finding that activating melanocortin systems potently counteracts binge drinking and 2) it represents one of the first clinical trials to investigate the efficacy of pharmacotherapy for binge drinking.* These innovations have the potential to affect clinical practice for the binge drinking patient.

Innovation 1. First proof of concept trial to translate to humans the preclinical finding that activation of melanocortin systems with/without μ -opioid receptor antagonism reduces binge drinking

Navarro et al (2015) recently demonstrated that activating melanocortin systems with/without opioid receptor antagonism in brain produced a powerful effect to reduce binge drinking in a mouse model. The rationale to test these systems derived from evidence that activation at the melanocortin receptor blunts ethanol intake in animals and that melanocortin peptides and the endogenous opioid β -endorphin share a common protein precursor and functional relationships (See Navarro et al, 2015).

In their study, Navarro et al (2015) used melanotan II (MT-II) to activate the melanocortin receptor and naltrexone for opioid blockade. MT-II reduced bring drinking with MT-II being more potent and overall more effective than naltrexone (72% decrease in ethanol consumption vs 47% decrease), Figure 1. Furthermore, MT-II increased the effectiveness of naltrexone in a synergistic manner. A key aspect of this study was that it investigated effects on binge-drinking rather than dependent level drinking, as the authors note “...our results specifically speak to the possibility that these targets could be useful for curbing excessive binge drinking, an approach that may be useful for preventing the transition to dependence.”

Advantageously, for human trials, Bupropion (Wellbutrin®), an FDA approved antidepressant and anti-nicotine agent, activates the melanocortin system through proopiomelanocortin neurons likely via norepinephrine and dopamine reuptake inhibition (Greenway et al, 2010; Hasegawa et al, 2005). Thus, we now have access to a pharmacological approach, bupropion + naltrexone, approved in humans to test the hypothesis that activation of melanocortin systems while blocking the opioid system will significantly reduce binge-drinking-- a true translational trial.

Innovation 2: One of the first clinical trials to investigate the efficacy of pharmacotherapy for binge drinking. As noted earlier, there has been very limited effort towards identifying pharmacological agents that help with binge drinking, particularly in younger populations. The O’Malley et al (2015) trial may be the first placebo-controlled trial in young (18-25 years), heavy drinkers and it did find evidence that naltrexone reduced drinks/drinking day. Given that the prevalence of binge drinking peaks in the 18-34 year age range and is commonly not associated with physical dependence it is important to conduct clinical trials in populations with these characteristics. The current proposal will therefore focus on subjects ages 21-44 years and will exclude those with overt physical dependence on alcohol.

Targeting the binge drinking population moves the field towards the concept of using pharmacotherapy to treat early phases of alcohol use disorders and potentially reduce the likelihood of individuals progressing from binge-drinking to overt physical dependence. While still a theoretical concept this is a highly innovative idea and one that could have profound implications for clinical management, see Thiele (2012).

Research Approach: For this feasibility/tolerability trial, it is important to use doses of bupropion and naltrexone that are known to be effective and safe for humans. For bupropion we have selected a 300 mg/d dose of the extended release formulation. The 300 mg dose of bupropion is approved by the FDA for depression and for nicotine dependence. The extended release 300 mg formulation has a lower estimated risk of seizures (0.1%) compared to the 0.4% rate for the immediate release formulation. The 0.1% risk of seizures

[figure not shown]

Figure 1: Effects of MT-II compared to naltrexone on binge drinking in mice (Navarro et al, 2015).

is comparable to the risk reported with other antidepressants such as sertraline and fluoxetine (FDA labels) and with acamprosate (FDA label), which is approved for alcohol dependence. Furthermore, we will be studying a binge drinking population without evidence of physical dependence, a history of seizures, or a reported history of cocaine use so seizure risk is minimized which has been raised as a concern based on animal studies (Silverstone et al, 2008). For naltrexone, we will use the standard dose of 50 mg/d used for alcohol use disorders..

Participants: 12 men and women between the ages of 21 and 44 years of age will be recruited from social media, e-mail list serve to UNC students and staff, and local newspaper/radio advertisements. **Key Inclusion criteria:** 1) A minimum of 5/3 (men/women) or more binge drinking episodes per month over the past three months (mean population values, CDC (2012)). A binge drinking episode is defined as the consumption of 5/4 (men/women) standard drinks (~12 gms ethanol) in about a two-hour period. Requiring multiple episodes of binge drinking over several months is important to identifying subjects with a consistent pattern of binge-drinking as shorter time frames may give misleading information (see Courtney and Polich, 2009). Subjects may meet DSM-V criteria for mild or moderate alcohol use disorder; 2) BMI ≥ 18.5 (normal weight or above); 3) express a desire to achieve abstinence or to reduce alcohol consumption. **Exclusion criteria:** 1) Presence of physical dependence on alcohol as assessed by clear tolerance to alcohol or alcohol withdrawal symptoms based on SCID interview or a Severe Alcohol Use Disorder (>5 SCID DSM-V symptoms); 2) a history of bulimia or a seizure disorder; 3) clinically significant medical disease that might interfere with the evaluation of the study medication or present a safety concern (e.g., renal insufficiency, cirrhosis, unstable hypertension, diabetes mellitus); 4) clinically significant psychiatric illness including any psychotic disorder, bipolar disorder, anorexia/bulimia, severe depression, or suicidal ideation; 5) other substance abuse or dependence disorder other than nicotine or occasional cannabis use; 6) Concurrent use of anticonvulsants, opioids, varenicline, MAOIs, any anti-alcohol medication or any psychotropic medication with the exception of stable doses of antidepressants for one month; prior history of adverse reaction to bupropion or naltrexone; 7) AST or ALT > 3.5 times ULN or bilirubin $> 1.5 \times$ ULN; 8) positive urine toxicology screen with the exception of cannabis. Individuals with positive cannabis screens will be excluded only if they have a history of a cannabis use disorder; 9) pregnancy or breastfeeding.

Trial Design: The design is an open-label trial. We will use standard clinical doses of bupropion-XL 300 mg/d (lower seizure risk) and naltrexone 50 mg/d dispensed by the UNC Investigational Drug Services. Bupropion XL will be initiated at 150 mg/d on Days 1-4 and increased to 300 mg/d for Days 5-84. Naltrexone will be initiated at 25 mg/d from Days 7-9 and then go to 50 mg/d for Days 10-84. We will see subjects at screening and then at Weeks 0, 1, 3, 5, 8 and 12. Subjects will be breathalyzed and receive Medical Management (MM) counseling to encourage compliance and progress towards drinking goals. MM is a medically oriented brief (10-15') therapy provided by medical personnel (MDs or nursing staff, only MDs in this trial). Our medical staff have been trained in MM and have been using it in other trials over the past five years. We will use the Time Line Follow-Back approach to assess alcohol consumption history modified to include time taken to consume alcohol and define a binge. We will also measure craving for alcohol using the Penn Alcohol Craving Scale.. We will assess tolerability by probing for adverse effects and will assess AST and ALT.

Our key outcomes of interest include tolerability and acceptability, drinking behavior including frequency and intensity of binge drinking, and craving for alcohol.

Recruitment, Telephone Screen, and Full Eligibility Screening: Subjects will initially be prescreened by phone and then at full screening read and sign the informed consent. A breathalyzer test will be administered (must be 0.00 gms/dl to give informed consent), height, weight and BMI recorded and a medical history and examination completed. Over-the-counter and prescription medication use will be recorded and nicotine use

Medical Management Intervention: The psychosocial support for the study will be Medical Management (MM) (Pettinati et al, 2005). Drs. [name], [name], [name] and [name] will conduct MM. Drs. [name] and [name] have been trained in MM by [name] and again by [name] of the University of Pennsylvania where [name] was trained as well. [name] has been trained in MM by [name]. MM sessions average 10-15 minutes and focus on three main areas: (1) feedback on consequences of drinking; (2) encouraging compliance with medication/addressing compliance problems and (3) encouraging progress towards drinking goal— reduction or abstinence are acceptable. 10% of sessions will be audiotaped and reviewed to enhance fidelity.

Medication Compliance Monitoring: Participants will record their pill taking in calendar-style diaries that will be provided and collected at each visit. Pills will be distributed in blister packs that will be returned to the study coordinator to reconcile any unused medication from the returned blister packs with participants' diary records.

Statistical Plan and Data Analysis: The primary outcomes of interest are rates of adverse events, reported tolerability and retention. Frequency and intensity of binge drinking and craving for alcohol will also be recorded. Because this is an open-label feasibility trial, no statistical analyses are proposed but rather an overall assessment of tolerability and feasibility will be obtained. Data will be entered into an Excel database and reviewed for accuracy.

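### The numbered exclusions do not clearly secure the absence of cocaine and seizure history that the protocol cites when it says bupropion seizure risk is minimized

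*Combined protocol and SAP*

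**What the plan says.** Research Approach defends bupropion 300 mg/d on seizure risk in two steps. The first is the choice of dose and extended-release formulation. The second concerns who will be treated: a binge-drinking population "without evidence of physical dependence, a history of seizures, or a reported history of cocaine use so seizure risk is minimized". The sentence adds that the concern comes from animal studies.

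The rules for entry are under Participants, in a numbered list of nine exclusions. Those that bear on these properties are:

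- Exclusion 1: "Presence of physical dependence on alcohol as assessed by clear tolerance to alcohol or alcohol withdrawal symptoms based on SCID interview".
- Exclusion 2: "a history of bulimia or a seizure disorder".
- Exclusion 3: "clinically significant medical disease that might interfere with the evaluation of the study medication or present a safety concern", with examples that do not include seizure.
- Exclusion 5: "other substance abuse or dependence disorder other than nicotine or occasional cannabis use".
- Exclusion 6: "Concurrent use of anticonvulsants, opioids, varenicline, MAOIs, any anti-alcohol medication", among other medications.
- Exclusion 8: a urine drug test positive for anything but cannabis, with a separate rule for people positive for cannabis.

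The paragraph on recruitment and full eligibility screening provides for a medical history and examination. In the text available it attaches no rule on past cocaine use or a past seizure to them.

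**The concern.** The safety rationale names three properties of the population and draws a conclusion from them. A reader expects each to be secured by an entry criterion, because that is what screening staff apply. One is. For the other two, the list uses narrower terms than the rationale: a substance disorder or a positive test instead of reported use, and a seizure disorder instead of a history of seizures.

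Seizure is the bupropion risk that the protocol itself singles out, and adverse events and tolerability are primary outcomes under Statistical Plan and Data Analysis. If the numbered list is what governs enrolment, a person could be dosed who lies outside the population on which the safety statement rests.

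**Working it through.** This is a check of text against text. The plan gives no figure to reproduce, so each property in the Research Approach sentence is compared with all nine exclusions.

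| Property in the rationale | Nearest exclusions | Result |
|---|---|---|
| No evidence of physical dependence | 1 | Matched |
| No reported history of cocaine use | 5, 8 | Not clearly covered for past use with no disorder and a negative test |
| No history of seizures | 2, with 1, 3 and 6 | Covered except for a narrow residual |

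**Cocaine.** Take a candidate who reports having used cocaine in the past, never had a disorder, and tests negative at screening.

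1. Exclusion 8 does not apply, because it depends on the test result at screening and not on history.
2. Exclusion 5 is built around the word disorder. On that reading it does not apply. Its exemption for occasional cannabis use suggests that the drafter may also have had use in mind, so it might reach current use of other drugs. It contains no reference to past use.
3. None of the other seven exclusions concerns non-alcohol substance use of this kind. Exclusion 6 concerns concurrent medication and earlier adverse reactions to the study drugs.

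The candidate falls outside the population in the rationale but is not clearly excluded by the list.

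**Seizures.** Take a candidate with one past seizure, no diagnosis of a seizure disorder and no treatment.

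1. In exclusion 2 the words about history can govern both nouns, so a past seizure disorder is reasonably read as excluded. A single seizure is not necessarily a disorder.
2. Exclusion 1 would take out someone whose seizure reflected alcohol withdrawal as assessed in the SCID interview. Exclusion 6 would take out anyone on anticonvulsants. Neither applies here.
3. Exclusion 3 could apply if the investigator judged the event to be clinically significant disease with a safety concern. That is discretion, not a stated rule.

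This gap is narrower than the one for cocaine.

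**Size.** The 0.1% seizure rate in the protocol belongs to the extended-release formulation. The documents give neither the number of candidates in either gap nor their seizure risk on bupropion, so no excess risk can be calculated.

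**The case against.** The strongest reply concerns exclusion 5. If it reached only diagnosed disorders, an exemption for occasional cannabis use would be unnecessary. The drafter may therefore have meant to exclude other drug use generally, sparing only nicotine and occasional cannabis. This stands in part: it makes the reach to current cocaine use ambiguous, and the gap cannot be called firm. It does not clearly extend to remote use.

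A second reply is that Research Approach is protocol text too, and states prospectively who will be studied. That is fair, and the list fails to repeat the statement rather than contradicting it. But if both are binding, the protocol holds two eligibility standards that differ, and they still need to be aligned. Only the inclusion criteria are headed as key ones. The exclusion list carries no such label, so nothing in the text points to further unlisted exclusions.

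A third reply is that history wording is used elsewhere in the list (for example "prior history of adverse reaction to bupropion or naltrexone" in exclusion 6), but that little can be read into its absence for cocaine. This is right. The drafting is loose, with bulimia in both exclusion 2 and exclusion 4, and the point does not depend on that inference.

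A reader might go further and infer that such people would in practice be enrolled. The documents do not support this. A medical history is planned, and the screening paragraph breaks off in this copy just as it reaches nicotine use, so how cocaine history is elicited cannot be judged.

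**Conclusion.** The point holds as a minor inconsistency, with moderate confidence. Of the three population properties offered in support of minimized seizure risk, one is secured by the exclusions. One is not clearly secured for past, non-disordered, test-negative cocaine use, and one is secured apart from an isolated past seizure.

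This assumes that the numbered list is the working rule at enrolment and that exclusion 5 is not read to cover remote use.

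A reader might also infer that participants face a raised seizure risk, or that the case for bupropion fails. Neither follows. The documents contain no rate for people in the gap, and the argument from dose and formulation stands on its own. The sample size of 12 is unaffected, and so is the analysis, which is descriptive with no tests planned.

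**What to change.** Add *reported history of cocaine use* to the exclusions, and reword exclusion 2 to *a history of bulimia, any history of seizures, or a seizure disorder*. Ask about both at the medical history already planned at full screening.

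The cost is two short wording changes and the loss of some candidates for the 12 places. The documents do not give that number, but it should be small, and these are people whom the rationale already says will not be studied.

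Narrowing the sentence in Research Approach instead would remove the mismatch on paper. It would also weaken the safety statement and leave unchanged who may be dosed, so it is not an adequate substitute.

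### As written, the stable-antidepressant exception in exclusion 6 also covers bupropion, so a current user is not barred and could take study bupropion 300 mg/d on top of their own supply

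*Combined protocol and SAP*

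**What the plan says.** Exclusion 6 (Participants section) begins with a list of barred concurrent drugs: "Concurrent use of anticonvulsants, opioids, varenicline, MAOIs, any anti-alcohol medication". It goes on to bar "any psychotropic medication with the exception of stable doses of antidepressants for one month". It closes with a bar on anyone with a "prior history of adverse reaction to bupropion or naltrexone", which is the only place where the exclusions name bupropion.

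Elsewhere the protocol places bupropion in the exempted class. Overall Concept reads "Because the antidepressant bupropion has been shown to activate melanocortin systems in brain", and Innovation 1 describes it as "an FDA approved antidepressant and anti-nicotine agent".

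Trial Design gives the study dosing: "Bupropion XL will be initiated at 150 mg/d on Days 1-4 and increased to 300 mg/d for Days 5-84". Research Approach justifies the 300 mg extended-release dose by an estimated seizure risk of 0.1%, against 0.4% for immediate release. The screening section has prescription and over-the-counter medication recorded but states no action on what is found. In the available text that sentence breaks off, so I infer nothing from what may follow it.

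**The concern.** An eligibility rule that exempts stable antidepressants, in a trial of an antidepressant, needs to say whether the study drug itself is exempt. This one does not, and its literal meaning is that it is. Because exclusion 6 governs concurrent use, the exempted drug is one the participant may go on taking during the trial.

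Two situations could follow, and they exclude each other:

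- **Add-on:** the participant keeps their own bupropion and takes study drug as well. Total dose then goes beyond the level for which the protocol offers a safety argument, in a trial that treats seizure risk as a reason for choosing formulation, dose and population.
- **Replacement:** study drug takes the place of their own supply. The dose is as planned, but the participant has already shown that they tolerate one of the two drugs, and adverse events, tolerability and retention are the primary outcomes.

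These push the adverse event and retention rates in different directions, so the direction of any bias is unclear. Dose safety is the main issue.

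**Working it through.** **Does the text admit a current user?**

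1. Bupropion is an antidepressant by the protocol's own description, in two places.
2. Exclusion 6 exempts antidepressants held at a stable dose for one month and removes no individual drug from that exemption. MAOIs are listed separately as barred, so the authors did single out one group of drugs by name; bupropion was not treated the same way.
3. The other study drug is covered. Background naltrexone falls under the ban on anti-alcohol medication, given Research Approach: "For naltrexone, we will use the standard dose of 50 mg/d used for alcohol use disorders". Of the two study drugs, only background bupropion is let through.
4. No other criterion closes the gap. Exclusion 3 concerns medical disease, and exclusion 4 removes severe depression but not milder depression. Exclusion 5 allows nicotine use disorder. Depression and nicotine dependence are the two indications Research Approach gives for bupropion 300 mg, so a current user who meets every other criterion is plausible.
5. Medication Compliance Monitoring reconciles dispensed blister packs with diaries and sets no limit on outside supply.

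**Total dose under add-on use**

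Inputs: study dose 150 mg/d on Days 1-4 and 300 mg/d on Days 5-84 (Trial Design). Own dose is not given; I assume 150 or 300 mg/d, the two levels the protocol names. Total = study dose + own dose.

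| Own dose (assumed) | Days 1-4 | Days 5-84 | Ratio to 300 mg/d, Days 5-84 | Days above 300 mg/d |
|---|---|---|---|---|
| 150 mg/d | 150 + 150 = 300 | 300 + 150 = 450 | 450/300 = 1.5 | 80 of 84 (95%) |
| 300 mg/d | 150 + 300 = 450 | 300 + 300 = 600 | 600/300 = 2.0 | 84 of 84 (100%) |

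Under replacement the total never exceeds 300 mg/d.

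**Effect on the primary rates**

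One participant is 1/12 = 8.3 percentage points of any rate, which bounds the effect of one such person. As an illustration only, assume a 30% event risk in the other 11 participants:

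- Replacement, assumed 10% risk in the user: (11 × 0.30 + 0.10)/12 = 28.3%, a shift of −1.7 points.
- Add-on, assumed 50% risk in the user: (11 × 0.30 + 0.50)/12 = 31.7%, a shift of +1.7 points.

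The two shifts are equal in size only because the assumed risks lie 20 points either side of 30%.

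**The case against.** The strongest reply is that add-on dosing needs a step the protocol never directs: a physician would have to see the participant's own bupropion and still add study drug. Medication is recorded at screening, a history and examination are taken, and only physicians deliver Medical Management. The dosing text also speaks of initiating bupropion and of standard clinical doses, which suggests a regimen started in people not already on the drug. On this view the point is a drafting ambiguity about a rare participant, worth a clarification and little more.

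Part of this stands. Existing use would probably be seen, which makes double dosing less likely. The documents give no prevalence of bupropion use and no seizure risk above 300 mg/d extended release, so the added risk cannot be quantified from them. The event-rate illustration rests on assumed values, and since no statistical analyses are planned, it changes no test or decision rule. The selection argument is also modest, because excluding people with a past adverse reaction already tilts the sample towards tolerators.

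None of this supplies a written bar. The dosing schedule describes study drug, not eligibility, and recording a medication is not a rule about it. Two investigators following the text could reasonably do three different things: exclude, substitute or add on. Where seizure risk is a stated concern, that should not be left to whoever happens to notice.

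**Conclusion.** The concern holds. Exclusion 6 is too broad as written: it does not bar a participant on stable bupropion, and nothing in the available text requires washout or substitution or caps total dose. With an assumed own dose of 150 to 300 mg/d, add-on use gives 450 to 600 mg/d on Days 5-84, beyond the dose that the protocol's safety argument covers. That argument would simply not apply to such a person; how much the risk rises cannot be said from the documents. The possible distortion of the primary rates is secondary: at most 8.3 points per person, with no settled direction. This should be fixed before enrolment proceeds, on grounds of dose safety. It does not invalidate the trial.

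**What to change.** In exclusion 6, insert 'other than bupropion' after 'antidepressants', so that the exemption covers only stable doses of other antidepressants. Bupropion then falls back under the general ban on psychotropic medication. The intended meaning should be that current use of any bupropion-containing product excludes.

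The change is three words. Doses, the sample size of 12, the outcomes and every other criterion stay as they are. The cost is a possible small loss of otherwise eligible recruits, of unknown size because the documents give no prevalence of bupropion use.
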